## **7.2. Subject ID assignment (Phase 1)**

The assignment of participant ID will be only applied in the study sites. Each patient enrolled in the evaluation will be given a subject ID. This subject ID will be independent of the patient's OPC ID, which is assigned to each individual when they are registered at the OPC. The subject ID will take the following format :<XX>-<YYY>

- XX: the letter code(s) assigned to each participating site using alphabetical letters.
- YYY: the number which is assigned to an individual patient. This part has three characters from 001 to 999.

Sequentially numbered subject IDs for each site will be printed and, after consent, assigned to each enrolled participant. A sticker with a pre-printed subject ID will be placed at the top of the first page of all case report forms (CRFs). Accurate records of assigned numbers will be kept and updated into Enrollment log at OPCs (see Appendix 14B: Enrollment Log for OPC) to ensure that no two patients are assigned the same subject ID. The study staff will be responsible for securing the patient's information and minimize the risk of re-identification of the subject.

In Phase 2, screened patients will be given a unique ID which is made of patient's name in abbreviation, age, and OPC code. This would allow the study team to identify patients with duplication of CrAg results and track patients with positive CrAg results for their uptake of fluconazole.

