**Phase 2:** From April 2017[projected] to September 2017, we will perform a cost and cost-effectiveness analysis of CrAg screening, and continue screening as a routine service at existing sites and expand to additional sites (preferentially to hospitals affiliated with Phase 1 OPCs and to other OPCs whose CD4 testing is conducted at laboratories already conducting CrAg screening as part of Phase 1). CrAg tests will also be made available to screen all patients with  $CD4 \leq 100 \text{ cells}/\mu\text{L}$  including those who are treatment-experienced. The test will also be made available for use among symptomatic patients for diagnostic purposes, including CSF and bloodtesting. We will monitor prevalence at each testing site, but screened patients will not be enrolled in longitudinal follow-up. Phase 2 will last for at least 6 months based on availability of funding and fluconazole for those who screen CrAg positive and the availability/stability of CD4 testing. [Note that follow up of patients enrolled in Phase 1 will continue during this time period, but is considered to be part of Phase 1 rather than Phase 2. Also, sites included in Phase 2 may

change over time as a results of the instability of CD4 testing (e.g., if participating laboratories stop conducting CD4 testing, those sites might no longer be included; if participating laboratories begin CD4 testing for other sites, those sites might be included).]

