### **7.1.2. CrAg screening in Phase 2**

In Phase 2, CrAg screening will be performed as a routine service, and physicians will not prescreen patients according to study eligibility criteria. Rather, all routine laboratory requisition forms from the participants sites will be pre-marked with a note to the laboratory to perform reflex CrAg screening on any specimen with a  $CD4 \leq 100 \text{ cells}/\mu\text{L}$ . Providers will have a checkbox to mark the indication for the CD4 test on the requisition form, i.e., whether the CD4 test is being ordered for (1) new enrollment; (2) routine monitoring; or (3) presumed treatment failure. Laboratories will use the LFA provided by the study to perform reflexive CrAg screening with study LFA on specimens from patients with  $CD4 \leq 100 \text{ cells}/\mu\text{L}$  or signs/symptoms of meningitis or among outpatient or hospitalized patients with WHO stage 3 or 4 diseases at the discretion of the provider.

Results of the CD4 and CrAg tests will be recorded daily by the participating laboratories, and results sent to the requesting OPC or hospital along with the CD4 count. All laboratories participating in Phase 2 will record the CD4 count, CrAg result, and indication for CrAg test along with the code for the requesting site and other data that are routinely included on the requisition form (typically age and birth year). Because Phase 2 is being implemented programmatically, laboratories will have the choice whether to incorporate the CRICS data (e.g., CrAg result and indication for CD4) in their routine laboratory logs or to use logs provided by CRICS. The data will be collected by the project team on a regular basis.

Under Phase 2, participating CRICS laboratories are expected to inform the corresponding OPCs or inpatients wards, as well as the project team, of any CrAg-positive results as soon as possible. The patient's primary providers are responsible for prescription of fluconazole and follow up according to their standard care procedures and national

guidelines. Fluconazole supply for identified CrAg-positive patients will be provided by the study if not readily available for the patient at the participating sites. We will monitor the prevalence of CrAg positivity through labs without enrolling patients into the study.

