### **13.3 Confidentiality**

No names will be recorded on CRFs; CRFs will contain both study IDs and the client number from the OPC medical record. Data will be entered onto electronic databases on password-protected computers, which will only be accessible to study personnel. Only study ID and not the participant's OPC medical record number or name will be entered into the database.

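### The Phase 2 patient ID relies on age and shares no key with the Phase 1 study ID, so retests can enter the pooled CrAg prevalence as new patients

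*Protocol*

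**What the plan says.** **Phase 2 ID.** Section 7.2 states that "screened patients will be given a unique ID which is made of patient's name in abbreviation, age, and OPC code". Its purpose is given in the next sentence: "This would allow the study team to identify patients with duplication of CrAg results". It also serves to track fluconazole uptake in positives.

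**Phase 1 ID.** "Each patient enrolled in the evaluation will be given a subject ID", made of site letters and a sequence number. "This subject ID will be independent of the patient's OPC ID". Section 13.3 adds: "Only study ID and not the participant's OPC medical record number or name will be entered into the database".

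**Who is tested in Phase 2.** Under section 7.1.2, requisition forms tell the laboratory to "perform reflex CrAg screening on any specimen with a" CD4 count of 100 or less, without eligibility prescreening. The form has a checkbox for the reason for the CD4 test: new enrollment, routine monitoring or presumed treatment failure. The Protocol Summary includes treatment-experienced patients.

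**Overlap of the phases.** The Protocol Summary notes that "follow up of patients enrolled in Phase 1 will continue during this time period". Table 4 in section 7.7 schedules CD4 tests at 6 and 12 months.

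**What is counted.** The part of section 3 on LFA use in Phase 2 has laboratories tally tests and results for the prevalence estimate. Section 6 takes both primary outcomes from the two phases together. The Protocol Summary sets the prevalence objective in patients newly enrolled in care. Table 1 omits that restriction but still defines the outcome as a proportion of patients.

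**The concern.** An ID meant to find duplicates should stay constant for one person and differ between people. This one does neither reliably. A patient tested before and after a birthday gets two IDs, and two patients of one clinic with the same initials and age get one.

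The larger gap lies between the phases. A Phase 1 participant whose monitoring CD4 is still ≤100 during Phase 2 is reflex-tested and receives a Phase 2 ID that does not show that the person was already counted. The protocol describes no matching across phases and no exclusion of repeat or monitoring tests from the pooled figure.

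At stake is a primary outcome built on few events, about 46 expected positives. A handful of recounted positives, or a block of repeat negatives, changes the estimate, and the confidence limits assume that each record is a different patient.

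**Working it through.** **1. The plan's own figure.** Inputs from section 6 and Table 3 are 1,972 patients with CD4 ≤100, 22 clinics, ICC 0.02 and prevalence 2.6%.
- m = 1,972/22 ≈ 90; DEFF = 1 + (90 − 1) × 0.02 = 2.78, as stated.
- Half-width = 1.96 × √(0.026 × 0.974 × 2.78 / 1,972) = 1.17 points.
- Limits are 1.43 to 3.77, which Table 3 gives as 1.40 to 3.80.

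The table reproduces, with every record treated as a distinct patient. The projected counts themselves give 46/1,972 = 2.33%, the baseline used below.

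**2. Phase 2 share.** 1,972 − 1,232 = 740 patients and 46 − 29 = 17 positives.

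**3. How often the ID changes.** Taking birthdays as spread evenly, two tests t months apart straddle a birthday with probability t/12. That is 25% at 3 months, 50% at 6 months and essentially all at 12 months. This concerns pairs of tests within Phase 2.

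**4. How many Phase 1 retests could occur (assumption).** At 74 enrolments per month (section 6), and timing visits roughly from enrolment:
- Month 12 falls in April to September 2017 for those enrolled April to September 2016: 6 × 74 = 444.
- Month 6 falls there for those enrolled October 2016 to March 2017. This is about 221 if the total is 1,104 (1,104 − 957 + 74), or 444 if enrolment stays at 74 per month.
- The total is 665 to 888 before deaths, losses and missing CD4 tests.

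The range used is 600 to 900 tests with 20% to 40% still ≤100. The documents do not give that share. Repeats are then 600 × 0.2 = 120 to 900 × 0.4 = 360.

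**5. Effect on the pooled prevalence.**

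| Positives among the repeats | 120 repeats | 360 repeats |
|---|---|---|
| none | 46/2,092 = 2.20% | 46/2,332 = 1.97% |
| 3 | 49/2,092 = 2.34% | 49/2,332 = 2.10% |
| all 29 Phase 1 positives (extreme) | 75/2,092 = 3.59% | 75/2,332 = 3.22% |

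**6. Direction.** Repeats raise the estimate only if more than 2.33% of them are positive. That means at least 3 of 120 (120 × 46/1,972 = 2.8) or at least 9 of 360 (360 × 46/1,972 = 8.4). The documents do not settle which side applies.

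**The case against.** The best defence is the reason-for-test checkbox in section 7.1.2, which section 10 says is collected with the result. A Phase 1 participant's 6- or 12-month CD4 is monitoring. Counting only new-enrollment tests would remove it without any common ID, and such a filter may sit in an analysis plan that is not shown. This stands in part. The safeguard exists, but the protocol gives duplicate detection to the ID, tallies tests, and nowhere ties the pooled estimate to that checkbox.

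A reader might infer that the two phases cannot be linked at all. The documents do not support that. Section 13.3 says "CRFs will contain both study IDs and the client number from the OPC medical record", clinics keep an enrollment log, date of birth is a Phase 1 baseline variable, and laboratories list screened patients by clinic. Positive results in Phase 2 also go to the project team, and only about 29 Phase 1 positives are expected, so a returning positive is the easiest repeat to notice. What holds is narrower: the IDs share no key and no matching step is planned.

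A reader might also infer a clear upward bias, because three recounted positives would move Phase 2 from 17/740 = 2.30% to 20/743 = 2.69%. That adds the positives without the negatives retested alongside them. With 120 to 360 repeats the figure is 20/860 = 2.33% to 20/1,100 = 1.82%.

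Finally, 600 to 900 retests is generous. Sections 1.2 and 5 describe CD4 testing as being scaled down, sometimes charged for and unstable. The birthday problem also affects few routine pairs inside a Phase 2 that section 3 puts at 3 to 6 months.

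**Conclusion.** The point holds as a minor but real weakness. The Phase 2 ID does not reliably do the job section 7.2 gives it, it has no common key with the Phase 1 ID, and nothing stated keeps Phase 1 retests out of a pooled estimate aimed at newly enrolled patients.

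Its size is illustrative only. It rests on the assumed 120 to 360 repeats and on reading age as age at each test, which is fair because Phase 2 demographics come from the requisition form. The pooled figure moves from 2.33% to between 1.97% and 2.34% with zero to three recounted positives. Even the extreme case of all 29 stays below the upper limit of 3.80. Lying inside the planned limits shows that the error is modest beside sampling error. It does not remove the bias, and the direction remains open.

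**What to change.** 1. In section 7.2, replace age with birth year in the Phase 2 ID and add sex where available. Section 7.1.2 says birth year is typically on the requisition, and section 10.1 lists both fields as collected when available.
2. State that prevalence counts the first result per person.
3. Restrict the pooled primary estimate to CD4 tests marked as new enrollment, which removes Phase 1 follow-up retests. Report monitoring and treatment-failure tests separately. Align the outcome wording in Table 1 with the objective in the Protocol Summary.

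**Cost.** A change to the ID rule and a short counting rule, using fields already on the forms. Birth year, sex or indication will be missing on some forms, and the primary count becomes somewhat smaller. Adding the clinic client number would strengthen matching but is optional. It is not among the listed Phase 2 fields, and would have to be reconciled with the de-identified data waiver in section 13.2 and the confidentiality text in section 13.3.

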## **7.3. Management of a negative CrAg result**

a. Phase 1: Patients  $CD4 \leq 100$  cells/ $\mu L$  who have a negative plasma CrAg result will be managed in accordance with national guidelines which include the assessment for other OIs, adherence preparation, and starting ART. They will be followed up for a minimum of 6 months and up to 12 months depending on the duration of the study period. Baseline data and follow-up data (2-.6-, and 12- month follow ups) will be collected on the enrollment and follow-up forms (see Appendix 4: Enrollment and Appendix 6: Follow-up ).

**b. Phase 2:** Patients are not enrolled for follow-up. No clinical data will be collected apart from CD4 count, indication for CD4 test, and CrAg result. In addition, we will document number tested, number who are CrAg positive, and the respective CD4 counts.

#### **7.4. Management of a positive CrAg result**

##### **a. Management of a CrAg-positive result - Phase 1**

###### **Asymptomatic patients**

Patients with a positive CrAg test, and who consent to study participation will undergo routine examination at the OPC including assessment for presence of symptoms of meningitis (see Appendix). Patients who are plasma CrAg-positive but do not have symptoms of meningitis will be started on high-dose fluconazole as treatment for early cryptococcal infection.

The optimal antifungal regimen in the population with isolated plasma CrAg remains to be determined.[11] The WHO Rapid Advice recommends that patients with isolated plasma CrAg-positivity should be treated with fluconazole 800 mg/day (or 12 mg/kg/day up to 800 mg/day if aged below 19 years) for two weeks, then 400 mg/day (or 6 mg/kg/day up to 400-800 mg/day if aged below 19 years) for eight weeks, and continued maintenance with fluconazole 200 mg/day is recommended [11]. In this program, maintenance fluconazole will be continued until  $CD4 > 200$  cells/ $\mu L$  for at least 6 months.

In Vietnam, the 150 mg tablet of fluconazole is the standard formulation and widely available for use in the national HIV treatment and care program for the treatment of CM. For this programmatic roll out, fluconazole dosage differs slightly from that recommended by the WHO recommendations but is in line with readily available formulations (150 mg tablets) in Vietnam, and with the updated national guidance [16]. The initial dosage of fluconazole in CrAg-positive patients therefore will be 900 mg taken each day for 2 weeks (WHO recommends 800mg). This will be followed by fluconazole 450 mg orally each day for 8 weeks. Finally, maintenance treatment with fluconazole 200mg orally each day will continue until  $CD4 > 200$  cells/ $\mu L$  for at least 6 months. In accordance with the 2016 WHO guidelines, if HIV viral load monitoring is not available, fluconazole treatment will be continued until patient is stable and adherent to ART and antifungal maintenance therapy for at least one year. If HIV viral load monitoring is available, fluconazole treatment will be continued until patient is stable and adherent to ART and antifungal maintenance treatment for at least one year and has a suppressed viral load. Maintenance treatment after 6 months will be supported by VAAC with dosage of 150 mg per day as same dose as recommended by national

guideline for treatment of cryptococcal meningitis during maintenance therapy. VAAC is responsible for coordinating ART and OIs drug throughout the country, and they commit to support a full supply of fluconazole for patients enrolled in the screening program. Study findings will inform supply chain and other fluconazole logistical issues. During treatment, development of adverse events (AEs) or side effects related to the use of this drug will be assessed during routine visits to each OPC and managed according to national protocols.

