### **Symptomatic patients**

Plasma CrAg-positivity in a person with symptoms consistent with meningitis increases the suspicion for CM. If symptoms of meningitis (e.g., fever, headache, stiff neck) are determined by the treating physician to be present in a CrAg-positive patient, the patient will be referred to the nearest hospital capable of performing an LP and CSF analysis according to national protocols. Data from the hospitalization will be collected for analysis (Appendix 7:

Hospitalization ); however, evaluation and treatment of study participants with symptoms of meningitis will be determined by the treating physician in accordance with national guidelines. Patients with laboratory-confirmed CM will receive induction, consolidation, and maintenance phase therapy as per the Vietnam National HIV Guidelines. These might include intravenous amphotericin B 0.7-1mg/kg/day or high-dose fluconazole for two weeks (induction phase), followed by fluconazole 900 mg/day for 8 weeks (consolidation phase). At the end of the consolidation phase, fluconazole 200mg/day will be prescribed as secondary prophylaxis until  $CD4 >200$  cells/ $\mu l$  for at least 6 months or after viral suppression. This is according to the national protocol and is not considered part of this evaluation [15, 16].

Symptomatic CrAg-positive patients who refuse to have an LP or in whom an LP cannot be done will be offered the same treatment as laboratory-confirmed cases of CM, as outlined in the National Guidelines. If the patient refuses treatment for CM, they will be given oral fluconazole at the same dosage/length as asymptomatic CrAg-positive patients as a final option.

Patients admitted for treatment of CM will remain in the study, and the study point to contact (POC) at the OPC will be responsible for keeping in contact with the hospital to monitor the progress and document the patient's outcome. The OPC staff will abstract information from the inpatient medical record and fill in the study Hospitalization Form (see Appendix)

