## Cryptococcal Retention In Care Study (CRICS)

evaluation **eight weeks later**, during which time a dose reduction in their fluconazole to 200 mg per day maintenance dose will be completed.

- Follow-up visits for fluconazole dose changes should occur 2 weeks after fluconazole initiation and then 8 weeks after. If these do not coincide with routine OPC appointment, then non-routine appointments should be made. Patients should be told the importance of coming back to the OPC at those designated times for fluconazole dose changes. CRICS evaluation will be conducted and follow-up data will be collected at these 2 types of follow-up visits.
- CRICS evaluation and follow-up data collection should also be collected at routinely scheduled OPC visits that occur at ART initiation (if not at one of the above follow up visits), 2-, 6- and 12-months after ART initiation. Therefore, all enrolled CrAg-positive patients will be re-evaluated at 2-week and 10-week after fluconazole initiation and 2-, 6-, and 12-month follow-up after ART initiation (referred to as CRICS's visit). The specific date of these CRICS's visits might be decided in consideration of the patients' regularly scheduled clinic visit. In these visits, a short follow-up form (see Appendix 6: Follow-up ) which incorporates information on current symptoms, side effects of fluconazole (if they are on fluconazole) and other clinical outcomes should be filled out.
- CrAg-negative patients will be re-evaluated at routinely scheduled visits for ART initiation and 2-, 6-, and 12-month follow-up visits. The follow-up data collection form should be filled for each of these visits.
- All visits will be documented using Appendix 18: Patient's visit logbook

Cryptococcal Retention In Care Study (CRICS)

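### In the visible text, section 7.4 gives asymptomatic CrAg-positive patients two unlinked stopping rules and two maintenance doses of fluconazole; Table 4 and the pregnancy-test age ranges also need reconciling

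*Protocol*

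**What the plan says.** All references are to the Protocol. Figure 1, the Phase 1 management chart, is not visible in the text at hand.

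- **Section 7.4, asymptomatic patients, CD4 rule.** "Finally, maintenance treatment with fluconazole 200mg orally each day will continue until" CD4 is above 200 cells/µL for at least 6 months. The preceding paragraph states the same CD4 rule for this programme.
- **Same subsection, one-year rule.** Citing WHO 2016 guidance, it says that without viral load monitoring "fluconazole treatment will be continued until patient is stable and adherent to ART and antifungal maintenance therapy for at least one year". Where monitoring exists, a suppressed viral load is required as well.
- **Same subsection, later dose.** "Maintenance treatment after 6 months will be supported by VAAC with dosage of 150 mg per day as same dose as recommended by national". The sentence ends by naming meningitis maintenance as the setting of that guidance.
- **Section 7.4, symptomatic patients (confirmed meningitis).** "At the end of the consolidation phase, fluconazole 200mg/day will be prescribed as secondary prophylaxis until" CD4 is above 200 "for at least 6 months or after viral suppression. This is according to the national protocol and is not considered part of this evaluation".
- **Section 7.7, follow-up visits.** The dose changes after two weeks to 450 mg. The patient returns eight weeks later, "during which time a dose reduction in their fluconazole to 200 mg per day maintenance dose will be completed". No later change is listed. Section 10 (overview) describes the same two steps and also ends at 200 mg.
- **Table 4.** One row for reducing the fluconazole dose, placed on the first day of the ninth week. The row does not say from when the weeks are counted.
- **Pregnancy testing of CrAg-positive women at enrolment.** Section 7.5 covers ages 18–49; section 9.1 covers those under 55.

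**The concern.** A site treating an asymptomatic CrAg-positive patient through maintenance has to know which dose applies and when treatment ends. Section 7.4 gives two answers to each question. Section 8.4 asks monitors to check that doses are changed as section 7.4 prescribes. For late maintenance the visible text gives them no single standard, so they could neither confirm compliance nor record a deviation.

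The sites will also hold different data. Section 1.2 reports that CD4 testing is being scaled down, with stock-outs and patient charges, and Table 4 lists viral load only where available. If each site applies the rule it has data for, similar patients may be treated differently. On pregnancy testing, one group of women is tested under one section and not under the other, for a drug that section 7.5 describes as teratogenic.

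**Working it through.** No sample-size or power formula is involved. The check sets the statements side by side, with short arithmetic for reach.

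1. **Do the two stopping rules cover the same patients?** The one-year rule has two branches, viral load monitoring available and not available. Together these cover everyone. The CD4 rule has no such condition, so it also covers everyone.

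2. **Can one rule be met without the other?** Yes. A patient who is stable, adherent and suppressed for a year but whose CD4 stays at or below 200 meets the one-year rule and never the CD4 rule. A patient with CD4 above 200 for 6 months whose viral load is monitored and unsuppressed meets the CD4 rule and not the other. The paragraph contains no and, or, or order of precedence. The symptomatic subsection does join its own conditions with or.

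3. **Do the two doses overlap?** One sentence sets 200 mg per day until the CD4 rule is met. Another sets 150 mg per day for maintenance after 6 months. A patient still on maintenance after 6 months who has not met the CD4 rule falls under both. The 6 months could run from the start of fluconazole, of ART or of maintenance; the text names none of these.

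4. **Is the reason for 150 mg consistent?** The asymptomatic subsection calls 150 mg the national guideline dose for meningitis maintenance. The symptomatic subsection gives 200 mg for meningitis maintenance and attributes it to the national protocol. Both attributions cannot be right as written.

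5. **Does Table 4 match the scheduled steps?** Sections 7.4, 7.7 and 10 give 2 weeks at the first dose and 8 weeks at the second. Counted from the start of fluconazole, the changes fall after week 2 and after week 2 + 8 = 10. The first day of the ninth week is the day after 8 completed weeks. From the start of fluconazole it matches neither change. Counted from the start of the 450 mg dose it matches the second: 2 + 8 = 10. Table 4 does not say which clock applies, and its own follow-up row uses 2 and 10 weeks.

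6. **Pregnancy testing.** Enrolment is from age 18. The ranges 18–49 and under 55 differ for women aged 50 to 54 only.

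7. **How many patients?** Section 6 reports 25 CrAg-positive among 957 enrolled: 25 / 957 = 2.6%. Applied to the projected 1,104 enrolled, 1,104 × 0.026 = 28.7, which reproduces the protocol's figure of about 29. Only those who reach maintenance are exposed to points 1 to 4.

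8. **When does the stopping conflict bite?** With ART started at 2 weeks as scheduled, follow-up to 12 months after ART ends at week 2 + 52 = 54. Maintenance starts after week 10, so a full year of adherence to it is complete no earlier than week 10 + 52 = 62, after follow-up. If the year were counted from ART start instead, it would end at week 54. A CD4 above 200 sustained over 6 months would be shown by the Table 4 tests at 6 and 12 months, again at the end of follow-up (assuming those tests are timed from ART).

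**The case against.** The strongest reply is that this is late-treatment wording with little bearing on the study's results. Much of that stands. On the scheduled timeline, stopping is mostly decided at or after the last study visit, and section 3 passes patients still on maintenance to routine sources at that point. The monitoring argument is therefore weak for the stopping rule and stronger for the two doses. Figure 1 may also link the rules; if it does, the text still has to agree with it.

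One could say that the WHO 2016 sentences replace the CD4 rule. The text does not say so, and it states the CD4 rule in the sentence directly before them. One could also say that the two national doses come from different guideline editions. However, the symptomatic subsection cites both national documents in the reference list for its statement.

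Some stronger readings are tempting but not supported:

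- **Tablets.** A reader might infer that 200 mg is impossible because the dosage "is in line with readily available formulations (150 mg tablets) in Vietnam". The text uses the tablet strength to explain the initial dose, 200 mg is the WHO figure quoted in the same subsection, and nothing says that only one strength is available.
- **Supplier.** A reader might infer a firm conflict between study supply for the duration of the study (sections 3 and 13.4.1) and support by VAAC, the national HIV/AIDS administration, after 6 months. Section 7.4 also says that VAAC coordinates these drugs nationally and commits to full supply for enrolled patients, so the two may coexist. The wording merits a check only.
- **Exact durations.** A reader might try to state how many weeks a patient spends under two doses or two stopping rules. Without defined clocks, such figures would rest on the reader's own assumptions.

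**Conclusion.** The point holds as a set of contradictions in the visible text: two unlinked stopping rules for the same patients, two maintenance doses with an undefined start for the second, two attributions of the national meningitis dose, and a Table 4 dose-reduction entry without a clock. The pregnancy-test age range is a separate and minor mismatch.

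The reach is limited. About 29 CrAg-positive patients are expected in Phase 1, and fewer will reach late maintenance. The number of CrAg-positive women aged 50 to 54 is not given and may be zero. Section 6 names the proportion with CD4 at or below 100 and CrAg prevalence as the two primary outcomes; neither depends on fluconazole maintenance. Twelve-month mortality, a primary objective in section 2, comes after treatment. The documents give no basis for quantifying an effect on it, and with the dose and stopping conflicts arising late, any effect is probably small.

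The conclusion assumes that Figure 1 does not already settle the dose and stopping questions. The timing statement assumes ART at 2 weeks and CD4 tests timed from ART. No view is taken on which dose, stopping rule or age limit is right.

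**What to change.** The sponsor and clinical investigators should reconcile both parts of section 7.4 (asymptomatic and symptomatic) with section 7.7, Table 4 and the section 10 overview, and check Figure 1 and the supply wording in sections 3 and 13.4.1 against the result. Sections 7.5 and 9.1 should be reconciled separately.

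The revised protocol should state:

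- one stopping rule for maintenance, with its conditions explicitly linked and the start of each clock defined;
- one maintenance dose for each period, with a defined start;
- one named clock for the dose-reduction visits, used in the text and in Table 4;
- one age range for pregnancy testing of CrAg-positive women.

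The cost is protocol wording and a memo to sites. The sample size and the section 6 primary outcomes are unchanged.
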